2.4 ANALYSIS TIMING

The primary analyses will be performed after the last Confirmed Disease Progression visit occurred. The results of the statistical analyses described in this SAP will be included in a Clinical Study Report (CSR).

The data collected before CCOD (Clinical Cut-off Date) will be included in the primary analysis. The primary efficacy analysis will be performed on the Treatment period, which is defined as being from the first infusion of treatment (day1) until:

The end of the Treatment Period will be the last visit date of any efficacy measurement at week 96 (including EDSS, MRI or PRO) or withdraw date.

The duration of the treatment period is calculated as

$$\text{End of Treatment Period} - \text{first infusion date} + 1.$$

An analysis update of data collected during Safety Follow-up period will be performed once the last patient completed the safety Follow-up period. An addendum to the CSR will include results of selected statistical analyses described in this SAP, if not available at the time of the primary CSR analysis (refer to LoPo for selection of analyses). For each data type collected during the follow-up period (refer to protocol Appendix 2: Follow-up Schedule of Assessments), only listing will be provided if less than 50 patients have data available.

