4.4 EFFICACY ANALYSIS

4.4.1 Primary Efficacy Endpoint

Protocol-defined event definition

The definition of a protocol-defined event of disease activity is the occurrence of at least one of the following individual events while on treatment with ocrelizumab:

- A protocol-defined relapse defined as an occurrence of new or worsening neurological symptoms attributable to MS. Symptoms must persist for > 24 hours and should not be attributable to confounding clinical factors (e.g., fever, infection, injury, adverse reactions to medications), and immediately be preceded by neurological stability for at least 30 days.
- 24-weeks CDP based on increase in EDSS while on treatment with ocrelizumab
- A new T1 Gd-enhanced lesion on MRI after week 8
- A new and/or enlarging T2 hyperintense lesion on MRI after week 8

The MRI activity will be calculated on the events starting from week 8 (baseline reset).

Patient without any of this protocol-defined event of disease activity will be considered as NEDA = Yes (no evidence of disease activity).

The primary endpoint, NEDA, as well as the related disease activities components and combinations listed below, will be evaluated on the mITT population based on the following analysis principles:

- Patients, who discontinued treatment prior week 96 due to death or lack of efficacy, will be considered as having evidence of disease activity at the time of treatment discontinuation (e.g NEDA="NO", Relapse="Yes" and CDP="Yes").
- Patients who discontinued treatment for reasons other than death or lack of efficacy with no evidence of disease activity at the time of early treatment discontinuation will be excluded from the analysis as their disease activity status cannot be ascertained.

This is further summarized in the table below:

Endpoint	Patients who discontinued treatment without related disease activities prior week 96 due to:	
	death or lack of efficacy	Other reason than death or lack of efficacy with no evidence of disease activity
NEDA	included with evidence of disease activity (NEDA=NO)	excluded
Relapse	included with evidence of disease activity (Relapse=Yes)	excluded

24-weeks CDP	included with evidence of disease activity (CDP="Yes")	
 • If discontinuation before confirmation, excluded • If discontinuation after confirmation, included when CDP="Yes"
T1 Gd-enhanced lesions after week 8	included with evidence of disease activity	excluded

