4.4.2 Secondary Efficacy Endpoints

For all continuous secondary efficacy endpoints, in addition to the model based analyses, they will also be summarized descriptively at each assessment visit. Analysis populations are specified for each endpoint.

4.4.2.1 Proportions of NEDA patients during the initial 24-week and the initial 48-week period

This endpoint will be analyzed on the mITT population using the same approaches as described above in Section 4.4.1, for the proportion of NEDA patients assessed during the initial 24-week period and during the initial 48-week period.

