4.4.2.2 Time to first protocol-defined event of disease activity

The analyses will include patients in the mITT population.

Patients with early study discontinuation before any disease activity event will be censored at the withdraw date, which is defined in Section 4.6.1. It will be imputed as having an event if discontinuation reason is lack of efficacy or death.

1) Kaplan-Meier analysis of time to first protocol-defined event (refer to section 4.4.1), with estimates (Greenwood 95% confidence intervals using a log-log transformation) of proportion of patients with NEDA determined at week 96 and week 104 (or time of the last event/censoring if that is before week 104). Kaplan-Meier plots will be produced up to the last available time of censoring or event.

2) Life-table analysis will be used to estimate the survival probability of time to first protocol-defined event, with estimates and Greenwood 95% confidence intervals using a log-log transformation by using time intervals which correspond to planned MRI assessments (weeks 24, 48 and 96). Thus, exact time of protocol-defined relapses and 24-weeks CDP will fall within MRI time intervals such as [week 8-week 24), [week 24-week 48), [week48-week96) and [week 96, -end of study]. Life-table plots will be produced.

Sample SAS code can be found below (SAS code is regarded as “draft” until fully validated at the analysis stage):

a) Binary method

```
ods output binomial=dataset BinomialTest=tpvalue;  
proc freq data=event ate;  
    tables eventyn / binomial (level='1') alpha=0.05;  
run;
```

b) Kaplan-Meier method

```
proc lifetest data=dataset method=km conftype=loglog outsurv=surv plots=none notable
STDERR;
time aval*eventyn(1);
run;
```

c) Life -Table method

```
proc lifetest data=dataset method=life conftype=loglog intervals=24 48 96 outsurv=surv
plots=none STDERR;
time aval*eventyn(1);
run;
```

4.4.2.3 Change in EDSS from baseline to week 96

EDSS (actual value, change, percentage change from baseline) will be summarized at each visit (up to week 96) for the ITT population. The change in the eight function scores from baseline up to week 96 will also be summarized for the ITT population.

Additionally, summary statistics will also be presented at week 96 for the following categories of change in EDSS:

- worsened (>0.5),
- stable ($-0.5, 0, 0.5$)
- improved (<-0.5)

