4.6.1 Exposure of Study Medication

Definitions

Dose: Ocrelizumab dose is given as one infusion or two infusions administered 2 weeks apart. Patients will be considered to have received a Dose of treatment if at least part of one infusion of that Dose (either Day 1 or Day 15 for dual infusions) was given. If a Dose is completely missed instead of delayed, the next dose number will be based on the number of previous doses received.

Treatment duration (in weeks) for a patient will be calculated as follows:

$$[(\text{Date of last contact}^* - \text{Date of first dose}) + 1] / 7$$

Treatment duration (in years) for a patient will be calculated as follows:

$$[(\text{Date of last contact}^* - \text{Date of first dose}) + 1] / 365.25$$

*Earliest 1) date of last contact from the study completion page or study early termination page

2) date of death

3) CCOD

Exposure Analysis

Exposure of ocrelizumab will be summarized using descriptive statistics with the following data:

- treatment duration (weeks),
- number of doses received (day 1 and day 15 infusions are considered as one dose)
- total cumulative dose (mg).

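### The primary NEDA rule keeps early leavers who had an event and deletes those who did not, and no planned binary Week-96 analysis retains the deleted patients or bounds their effect

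*SAP*

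**What the plan says.** SAP 4.4.1 treats early treatment stops in two ways. Stops for death or lack of efficacy count as disease activity. Patients who stop for any other reason (other-reason leavers below) "with no evidence of disease activity at the time of early treatment discontinuation will be excluded from the analysis", on the ground that their status is unknown. An other-reason leaver who already had an event is not covered by that exclusion and stays in as NEDA=No; the CDP row of the table in 4.4.1 says so for confirmed progression.

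The rule reaches beyond the headline figure. The primary endpoint, "as well as the related disease activities components and combinations listed below, will be evaluated on the mITT population", follows the same principles. For Week 24 and Week 48 NEDA, SAP 4.4.2.1 states: "This endpoint will be analyzed on the mITT population using the same approaches as described above in Section 4.4.1".

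The time-to-event analysis in SAP 4.4.2.2 handles the same people differently: "Patients with early study discontinuation before any disease activity event will be censored at the withdraw date, which is defined in Section 4.6.1". It reads off "NEDA determined at week 96 and week 104 (or time of the last event/censoring if that is before week 104" and uses life-table intervals that end with "week48-week96) and [week 96, -end of study". Section 4.6.1 does not define a withdrawal date. For exposure it gives the earliest of "date of last contact from the study completion page or study early termination page", death and clinical cut-off. SAP 2.4 ends the treatment period at "the last visit date of any efficacy measurement at week 96 (including EDSS, MRI or PRO) or withdraw date", again without a definition.

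SAP section 4 says that it supersedes the protocol, which placed the primary analysis on all dosed patients and left missing data to the SAP.

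**The concern.** Among other-reason leavers, failures enter both the denominator and the NEDA=No count, while patients still event-free are removed from both. An unknown Week-96 status is a reason to censor or impute. It does not justify keeping a patient only when the answer is unfavourable.

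The study has one arm, so no comparator cancels the distortion. The NEDA proportion is the headline result, and its exact interval would be centred on the wrong value. The planned binary alternatives do not help a reader judge the effect. Sensitivity analysis A drops every early leaver. B to E change the event, relapse or MRI definition and keep the exclusion. The per-protocol set requires 96 weeks of treatment. The time-to-event analyses do keep these patients, but their date rules are not yet usable.

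**Working it through.** **The plan's own figure.** SAP 2.3: 750 patients, 30% observed. Clopper-Pearson for 225/750 gives 26.74% to 33.42%, half-width 3.34. This reproduces the stated 26.7% to 33.4% and 3.3 points.

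**Inputs.** N = 750 and p = 30% (SAP 2.3). The documents give no dropout rate for this trial. The nearest figure is 3.5% adverse-event discontinuation in the pooled relapsing-MS Phase III studies (Protocol 1.2), which is not all-cause. I assume other-reason dropout d = 5%, 10% and 20% by Week 96, with constant event and dropout hazards, independent of each other. Lack-of-efficacy and death stops are left out of the illustration.

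**Formulas.** λ = −ln p and μ = −ln(1−d).
- Share deleted = μ/(λ+μ) × [1 − p(1−d)]
- Expected primary estimate = p(1−d) / (1 − share deleted)

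**Worked case, p = 30%, d = 10%.** λ = 1.204 and μ = 0.105. Share deleted = 0.105/1.309 × (1 − 0.27) = 0.0587, about 44 patients. Leavers kept with an event: 75 − 44 = 31. Event-free completers: 0.27 × 750 = 202.5. Estimate = 202.5/705.9 = 28.7%, a bias of −1.3 points.

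| d | deleted | estimate (true 30%) | bias | deleted all No | deleted all Yes |
|---|---|---|---|---|---|
| 5% | 22 | 29.4% | −0.6 | 28.5% | 31.4% |
| 10% | 44 | 28.7% | −1.3 | 27.0% | 32.9% |
| 20% | 89 | 27.2% | −2.8 | 24.0% | 35.9% |

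At a true 50% the estimates are 49.3%, 48.5% and 46.8%. A simulation that detects MRI events only at Weeks 24, 48 and 96 gives similar biases at 30%: −1.1 to −1.3 at 10% dropout and −2.2 to −2.8 at 20%.

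**Sensitivity analysis A, same assumptions.** Completers only: 202.5/675 = 30.0%. The gap from 28.7% is the bias.

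**Informative leaving, d = 10%, completers at 30%, leaving times even over 96 weeks.** For leavers with Week-96 NEDA q, the average event-free probability at leaving is (1−q)/(−ln q).
- Hazard doubled: q = 0.09, truth = 0.27 + 0.1 × 0.09 = 27.9%. Average = 0.378, so the estimate is 0.27/(0.9 + 0.1 × 0.622) = 28.1%, bias +0.2.
- Hazard halved: q = 0.548, truth = 32.5%. Average = 0.751, so the estimate is 0.27/(0.9 + 0.1 × 0.249) = 29.2%, bias −3.3.

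The corresponding large-sample Kaplan-Meier biases are +0.8 and −1.3.

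**Kaplan-Meier and the censoring date.** Censored at treatment stop, the simulation gives 29.6% to 30.0% at 10% dropout. Treatment leavers are followed for at least 96 more weeks (SAP section 2). If 4.6.1 is read literally as last contact, they can remain at risk past Week 96 while their events count only on treatment. The estimate then rises to 32.8% to 33.7%. This is an upper case in which every leaver stays in follow-up past Week 96.

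**Kaplan-Meier and the Week-96 scan.** SAP Appendix 2 allows ±14 days around Week 96. The third life-table interval is open at Week 96, and nothing in 4.4.2.2 moves a scan to its nominal week. A lesion found at an in-window scan on or after Week 96 is therefore left out of the life-table estimate; one found after Week 96 is left out of the Week-96 Kaplan-Meier reading. Both omissions push the estimate up.

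**The case against.** The best defence is that analysis A is already planned. It has no outcome-dependent selection, so if leaving is unrelated to disease, setting it beside the primary result would expose the bias. This stands. It would be wrong to infer that nothing planned reveals the problem. Two limits remain. A also drops lack-of-efficacy and death leavers, all NEDA=No in the primary, so part of any gap has another cause. And A neither keeps the event-free leavers nor bounds what their outcomes could have been.

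The size rests on assumed dropout. At 5% the bias is about a fifth of the half-width and, under independent leaving, in the conservative direction. The analysis is descriptive and no decision depends on it. These points limit the importance but do not repair the rule.

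One conditional analysis does keep event-free leavers: the logistic fallback for T1 Gd-enhanced lesions in SAP 4.4.2.10. It does not concern NEDA.

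Four stronger readings are tempting and not supported:
- That Kaplan-Meier must replace the primary. It also assumes uninformative leaving, and with doubled hazard in leavers it does worse here (+0.8 against +0.2). The choice is a trade-off between estimators.
- That the dating of CDP is missing. SAP 4.4.2.7 analyses time to onset, and 4.4.1 separates initial progression from its confirmation, so dating at onset is implied.
- That the Week-104 reading is wrong by a known amount. This requires completers to be censored at their Week-96 visit. SAP 2.4 suggests that, but 4.4.2.2 does not say it, and its last interval runs to the end of the study. The size of the Week-96 scan error likewise depends on how visits spread within the window.
- That last contact is the intended censoring date. SAP 2.4 and the on-treatment event definition point to treatment stop. The flaw is that the text allows either reading.

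**Conclusion.** Wrong as written. The primary rule selects other-reason leavers on their outcome, and Week 24 and 48 NEDA and the 4.4.1 components inherit it. With leaving unrelated to disease and a true 30%, the expected bias is about −0.6, −1.3 and −2.8 points at 5%, 10% and 20% other-reason dropout: small at the low end, close to the 3.3-point half-width at the high end. With informative leaving the sign can change. The rule itself is certain from the text; the sizes are illustrations over an assumed range. The problem is bias rather than precision, since the half-width at 30% only moves from 3.34 to 3.46 at 20% dropout. The consequence is an off-centre headline estimate in an exploratory study, without the range that a reader needs. This should be fixed before database lock.

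**What to change.** 1. In SAP 4.4.4, add a binary NEDA analysis that retains the excluded patients: all NEDA=No as a lower limit and all NEDA=Yes as an upper limit, and/or multiple imputation.
2. Report the mITT Kaplan-Meier NEDA estimate at Week 96 beside the binary proportion, and likewise at Weeks 24 and 48. The Clopper-Pearson proportion may remain primary.
3. In SAP 4.4.2.2, censor event-free other-reason leavers at a defined date of treatment discontinuation and correct the reference to 4.6.1. Make treatment discontinuation the trigger, as in 4.4.1. Assign scheduled MRI events to nominal Weeks 24, 48 and 96, and include Week 96 in the third life-table interval.
4. Count any lesion on an on-treatment scan after Week 8 as an event, including one on the discontinuation scan, in line with 4.4.1, which sets no visit window. Make sure that the censoring date does not precede and so discard it. These scans find lesions earlier: at 20% dropout the simulated Kaplan-Meier estimate is 29.1% to 29.6% with them, against 30.0% without.

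The cost is text in SAP 4.4.1, 4.4.2.1, 4.4.2.2 and 4.4.4, date handling in an analysis already planned, and a few extra runs. The headline figure will carry a visible range. No patients or procedures are added.

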### **4.5.4 Neurological Examinations**

Neurological examinations will be used to distinguish relapse in MS from another neurological (non-MS) disorder. MS relapses should be recorded throughout the treatment period on a dedicated MS relapse eCRF page. See [Appendix 1](#) (Schedule of Assessments) for the timing of these assessments.

A protocol-defined MS relapse is an occurrence of new or worsening neurological symptoms attributable to MS that meets the following criteria:

- Symptoms must persist for >24 hours and should not be attributable to confounding clinical factors (e.g., fever, infection, injury, adverse reactions to medications)
- Symptoms should be preceded by neurological stability for at least 30 days
- Symptoms should be accompanied by new objective neurological worsening determined with a timely EDSS/ Functional Systems Score (FSS) assessment, consistent with an increase of at least:
  - $\geq 0.5$  points on EDSS scale
  - or  $\geq 2$  points on one of the following FSS scales: pyramidal, ambulation, cerebellar, brainstem, sensory, or visual
  - or  $\geq 1$  point on two or more of the following FSS scales: pyramidal, ambulation, cerebellar, brainstem, sensory, or visual

Episodic spasms, sexual dysfunction, fatigue, mood change or bladder or bowel urgency or incontinence will not suffice to establish a relapse (Please note: Sexual dysfunction and fatigue need not be scored).

All patients with new neurological symptoms suggestive of a relapse should have an EDSS/FSS assessment performed **as soon as possible, ideally within 7 days of the onset of symptoms**. EDSS/FSS data is needed to allow the Sponsor to confirm whether the reported clinical relapse meets the criteria for a Protocol-defined relapse.

Please note: All MS relapses (i.e., regardless of whether they may meet criteria for a protocol-defined relapse which will be adjudicated by the Sponsor based on the above criteria) will be recorded on a pre-specified eCRF “MS relapse” form.

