#### **4.5.6 Assessment of Disability**

Disability in MS will be measured by the EDSS. See [Appendix 1](#) (Schedule of Assessments) for the timing of these assessments.

The EDSS is based on a standard neurological examination, incorporating seven functional systems (pyramidal, cerebellar, brainstem, sensory, bowel and bladder, visual, and cerebral [or mental], plus “other”) rated and scored as FSSs. Each FSS is an ordinal clinical rating scale ranging from 0 to 5 or 6. These ratings are then used in conjunction with observations and information concerning ambulation and use of assistive devices to determine the EDSS score. The EDSS is a disability scale that ranges in 0.5-point steps from 0 (normal) to 10 (death) (see [Appendix 3](#)).

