## Appendix 3: Expanded Disability Status Scale (EDSS)

### Kurtzke Expanded Disability Status Scale (EDSS)

- 0.0 - Normal neurological exam (all grade 0 in all Functional System (FS) scores\*).
- 1.0 - No disability, minimal signs in one FS\* (i.e., grade 1).
- 1.5 - No disability, minimal signs in more than one FS\* (more than 1 FS grade 1).
- 2.0 - Minimal disability in one FS (one FS grade 2, others 0 or 1).
- 2.5 - Minimal disability in two FS (two FS grade 2, others 0 or 1).
- 3.0 - Moderate disability in one FS (one FS grade 3, others 0 or 1) or mild disability in three or four FS (three or four FS grade 2, others 0 or 1) though fully ambulatory.
- 3.5 - Fully ambulatory but with moderate disability in one FS (one grade 3) and one or two FS grade 2; or two FS grade 3 (others 0 or 1) or five grade 2 (others 0 or 1).
- 4.0 - Fully ambulatory without aid, self-sufficient, up and about some 12 hours a day despite relatively severe disability consisting of one FS grade 4 (others 0 or 1), or combination of lesser grades exceeding limits of previous steps; able to walk without aid or rest some 500 meters.
- 4.5 - Fully ambulatory without aid, up and about much of the day, able to work a full day, may otherwise have some limitation of full activity or require minimal assistance; characterized by relatively severe disability usually consisting of one FS grade 4 (others 0 or 1) or combinations of lesser grades exceeding limits of previous steps; able to walk without aid or rest some 300 meters.
- 5.0 - Ambulatory without aid or rest for about 200 meters; disability severe enough to impair full daily activities (e.g., to work a full day without special provisions); (Usual FS equivalents are one grade 5 alone, others 0 or 1; or combinations of lesser grades usually exceeding specifications for step 4.0).
- 5.5 - Ambulatory without aid for about 100 meters; disability severe enough to preclude full daily activities; (Usual FS equivalents are one grade 5 alone, others 0 or 1; or combination of lesser grades usually exceeding those for step 4.0).
- 6.0 - Intermittent or unilateral constant assistance (cane, crutch, brace) required to walk about 100 meters with or without resting; (Usual FS equivalents are combinations with more than two FS grade 3+).

- 6.5 - Constant bilateral assistance (canes, crutches, braces) required to walk about 20 meters without resting; (Usual FS equivalents are combinations with more than two FS grade 3+).

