- 7.0 - Unable to walk beyond approximately 5 meters even with aid, essentially restricted to wheelchair; wheels self in standard wheelchair and transfers alone; up and about in wheelchair some 12 hours a day; (Usual FS equivalents are combinations with more than one FS grade 4+; very rarely pyramidal grade 5 alone).
- 7.5 - Unable to take more than a few steps; restricted to wheelchair; may need aid in transfer; wheels self but cannot carry on in standard wheelchair a full day; May require motorized wheelchair; (Usual FS equivalents are combinations with more than one FS grade 4+).
- 8.0 - Essentially restricted to bed or chair or perambulated in wheelchair, but may be out of bed itself much of the day; retains many self-care functions; generally has effective use of arms; (Usual FS equivalents are combinations, generally grade 4+ in several systems).
- 8.5 - Essentially restricted to bed much of day; has some effective use of arm(s); retains some self-care functions; (Usual FS equivalents are combinations, generally 4+ in several systems).
- 9.0 - Helpless bed patient; can communicate and eat; (Usual FS equivalents are combinations, mostly grade 4+).
- 9.5 - Totally helpless bed patient; unable to communicate effectively or eat/swallow; (Usual FS equivalents are combinations, almost all grade 4+).
- 10.0 - Death due to MS.

---

\*Excludes cerebral function grade 1.

Note 1: EDSS steps 1.0 to 4.5 refer to patients who are fully ambulatory and the precise step number is defined by the Functional System score(s). EDSS steps 5.0 to 9.5 are defined by the impairment to ambulation and usual equivalents in Functional Systems scores are provided.

Note 2: EDSS should not change by 1.0 step unless there is a change in the same direction of at least one step in at least one FS.

Sources: Kurtzke JF. Rating neurologic impairment in multiple sclerosis: an expanded disability status scale (EDSS). *Neurology*. 1983 Nov;33(11):1444-52.

Source: [http://www.nationalmssociety.org/For-Professionals/Researchers/Resources-for-Researchers/Clinical-Study-Measures/Functional-Systems-Scores-\(FSS\)-and-Expanded-Disab](http://www.nationalmssociety.org/For-Professionals/Researchers/Resources-for-Researchers/Clinical-Study-Measures/Functional-Systems-Scores-(FSS)-and-Expanded-Disab)

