New/enlarging T2 lesions after week 8	included with evidence of disease activity	excluded

Analysis of binary NEDA

The proportions of patients with:

- NEDA
- Treatment discontinuation due to lack of efficacy or death without events prior the withdrawal
- Relapses
- No Relapse
- 24-weeks CDP
- No 24 weeks CDP
- T1 Gd-enhanced lesions after week 8
- No T1 Gd-enhanced lesions after week 8
- New/enlarging T2 lesions after week 8
- No New/enlarging T2 lesions after week 8
- MRI activity (T1 Gd-enhanced lesions or new/enlarging T2 lesions)
- No MRI activity
- Relapses or MRI activity
- 24-weeks CDP or MRI activity
- Clinical activity (Relapses or 24-weeks CDP)
- No clinical activity
- Relapses and MRI activity
- 24-weeks CDP and MRI activity
- Relapses and 24-weeks CDP

post-baseline up to the Week 96 visit will be calculated and presented with a two-sided 95% Clopper-Pearson exact confidence interval.

Protocol-Defined Relapse definition

A protocol-defined MS relapse is an occurrence of new or worsening neurological symptoms attributable to MS that meets the following criteria:

- Symptoms must persist for >24 hours and should not be attributable to confounding clinical factors (e.g., fever, infection, injury, adverse reactions to medications)
- Symptoms should be preceded by neurological stability for at least 30 days
- Symptoms should be accompanied by new objective neurological worsening determined with a timely EDSS/ Functional Systems Score (FSS) assessment, consistent with an increase of at least:
 - ≥ 0.5 points on EDSS scale
 - or ≥ 2 points on one of the following FSS scales: pyramidal, ambulation, cerebellar, brainstem, sensory, or visual
 - or ≥ 1 point on two or more of the following FSS scales: pyramidal, ambulation, cerebellar, brainstem, sensory, or visual

Information related to a PDR will be captured on a clinical relapse event case report form (CRF) page (Multiple Sclerosis Relapse). If the following criteria are satisfied, the clinical relapse will qualify as a PDR:

1. Clinical relapse is reported on eCRF.
2. Check-box of “Did symptoms persist for >24 hours and were not being attributable...” on the Clinical MS relapse event is checked.

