3. Check if the first EDSS assessment at a visit (unscheduled or scheduled) on or after the onset date of the relapse is increased by ≥ 0.5 steps from the previous EDSS; or selected FSS domains relevant to the relapse event (pyramidal, ambulation, cerebellar, brainstem, sensory, or converted visual) are increased by ≥ 2 points on one domain or ≥ 1 point on two or more domains. When deriving this step do the following:
 - Take the last EDSS/FSS score before each clinical relapse onset date
 - Take the first EDSS/FSS score on or after each clinical relapse onset date
 - Calculate the difference between the two scores
 - Select clinical relapses where there is an increase of ≥ 0.5 in EDSS or ≥ 2 on one appropriate FSS domain or ≥ 1 on two or more appropriate FSS domains
4. For each relapse that satisfies the 3 criteria above, check if the following relapses are within 30 days (i.e., the onset dates are ≤ 30 days apart). If they are within 30 days, then the later relapses are not PDR.

24-Week Confirmed Disability Progression (CDP) definition

Disability Progression as measured by EDSS is defined a ≥ 1 -point increase in EDSS score from a baseline EDSS score of 0.0–5.5 inclusive, and a 0.5-increase from a baseline EDSS score higher than 5.5. Because of the variability of EDSS, a single measurement at the baseline visit might not provide a sufficiently reliable baseline EDSS. Therefore, using an average score from two separate measurements may improve the reliability of baseline EDSS and the reliability of confirmed disability progression seen in the study. In the analysis of CDP, baseline EDSS is defined as the average of the EDSS scores at the screening and baseline visits (of note, any baseline visits occurring after the first dosing date will be disregarded in the computation of the baseline EDSS score), without rounding. If one of the EDSS scores from the screening or baseline visit was missing, the other was used for baseline EDSS.

Initial progression can happen at any scheduled or unscheduled visit during the 96-week treatment period.

An initial disability progression becomes confirmed if the following conditions are met:

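### SAP 4.4.1 omits the protocol's symptom exclusion from its relapse algorithm, so a bladder- or bowel-only episode can count as a protocol-defined relapse through the EDSS route

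*SAP*

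**What the plan says.** Protocol 4.5.4 gives three ways to show objective worsening: EDSS up by at least 0.5, one listed functional-system score up by at least 2, or two or more up by at least 1. It then limits all three: "Episodic spasms, sexual dysfunction, fatigue, mood change or bladder or bowel urgency or incontinence will not suffice to establish a relapse". The protocol synopsis has the same sentence, and so does the copy of that synopsis in SAP Appendix 1.

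The main text of SAP 4.4.1 repeats the three routes but not the limiting sentence. It then sets out four steps under the statement "If the following criteria are satisfied, the clinical relapse will qualify as a PDR":

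1. A relapse is reported on the eCRF.
2. The box on duration over 24 hours and attributability is ticked.
3. The score has worsened: "Select clinical relapses where there is an increase of ≥ 0.5 in EDSS or ≥ 2 on one appropriate FSS domain", or at least 1 point on two or more such domains.
4. Later relapses with onset within 30 days are dropped.

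The functional-system part of step 3 is confined to "pyramidal, ambulation, cerebellar, brainstem, sensory, or converted visual". The EDSS part has no such limit. SAP section 4 says that its analyses take precedence over those in the protocol.

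**The concern.** None of the four steps looks at what kind of symptom was reported. The six-domain list keeps bladder, bowel and cerebral changes out of the functional-system route. Total EDSS lets them back in, and the sentence that should stop this is missing. A programmer working from SAP 4.4.1 and one working from Protocol 4.5.4 could derive different relapse counts from the same data.

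The relapse flag feeds NEDA at Week 96, NEDA at Weeks 24 and 48, time to first event of disease activity, the annualized relapse rate (ARR), time to first protocol-defined relapse, and relapse severity. Steps 1 to 3 also decide which visits may confirm disability progression (CDP). None of sensitivity analyses A to E isolates the problem. Analysis C moves the other way by counting every reported clinical relapse.

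**Working it through.** **Can a bladder- or bowel-only episode pass step 3?**

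- Protocol 4.5.6 builds EDSS on "seven functional systems (pyramidal, cerebellar, brainstem, sensory, bowel and bladder, visual, and cerebral [or mental"], so bowel and bladder feed the total score.
- Entry requires a screening EDSS of 0.0 to 4.0. For steps 1.0 to 4.5, Appendix 3 Note 1 says "the precise step number is defined by the Functional System score(s").
- One system at grade 2 with the others at 0 or 1 is EDSS 2.0. EDSS 2.5 is "Minimal disability in two FS (two FS grade 2, others 0 or 1"). If the bladder score rises to grade 2 and nothing else changes, EDSS goes from 2.0 to 2.5, a rise of 0.5.
- Lower on the scale, a single bladder grade 1 moves EDSS from 0.0 to 1.0, and a second system at grade 1 moves it from 1.0 to 1.5. The footnote at these steps sets aside only cerebral grade 1.

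The episode therefore passes step 3. The documents do not reproduce the functional-system grading rules. That urgency or incontinence is scored under bowel and bladder is inferred from the system's name.

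**The plan's precision figure.** The exact Clopper-Pearson interval for 225/750 (30%) is 26.74% to 33.42%, half-width 3.34 points. This reproduces the stated 26.7% to 33.4% and 3.3.

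**Effect of m misclassified patients.** Here m is the number of patients whose only event is an excluded episode. Observed NEDA = (225 − m)/750, taking true NEDA as 30% and N = 750 as in the sample-size section. The analysed number will be somewhat smaller after the SAP's exclusions.

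| m | Observed NEDA | 95% CI |
|---|---|---|
| 4 | 29.5% | 26.2 to 32.9 |
| 8 | 28.9% | 25.7 to 32.3 |
| 15 | 28.0% | 24.8 to 31.4 |
| 25 | 26.7% | 23.5 to 29.99 |

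**How large might m be?** The documents do not say. Assume:

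- r, the share of patients reporting a relapse over 96 weeks: 10% to 30%.
- e, the share of those with excluded symptoms only and EDSS up by at least 0.5: 3% to 10%.
- q, the share of those with no CDP, MRI activity or other qualifying relapse. For illustration q = 30%, the planning NEDA rate, assuming independence. The upper limit is q = 1.

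Misclassified on relapse = r × e: 0.10 × 0.03 = 0.3% to 0.30 × 0.10 = 3.0%.

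Wrongly NEDA=No = r × e × q: 0.003 × 0.30 = 0.09% to 0.03 × 0.30 = 0.9%, or about 0.7 to 6.8 of 750 patients. With q = 1 it is 0.3% to 3.0%, or about 2 to 23 patients.

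**ARR.** The unadjusted rate is a count divided by exposure. If a share k of counted relapses is of this kind, the rate is too high by the factor 1/(1 − k). Using 3% to 10% for k, again an assumption, the factor is 1.03 to 1.11.

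**The case against.** The strongest reply is that the gap may be closed elsewhere. Protocol 4.5.4 says the sponsor adjudicates relapses against the protocol criteria, which include the exclusion. Protocol 5.3.5.10 sends isolated MS symptoms short of a full relapse to the adverse event form, so some episodes would never meet step 1. The sentence also survives in SAP Appendix 1, and the SAP cuts short the check-box wording, so the eCRF itself may screen symptom type. These points may well reduce the number of events, but they do not close the gap. SAP 4.4.1 derives the flag from data and mentions no adjudication, the adverse event routing rests on the investigator's judgement, and the eCRF is not in the documents.

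The EDSS route of 0.5 or more is also the protocol's own. That stands: the route is not the error, only the missing exclusion is.

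A reader might infer that fatigue, mood and spasm episodes are counted in the same way. The documents do not support that. Fatigue and sexual dysfunction need not be scored, cerebral grade 1 is set aside at the lowest EDSS steps, and nothing shows a scored item through which episodic spasms alone raise EDSS. The route is clear only for bladder and bowel.

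The effect can also be bounded from planned output. SAP 4.4.1 reports the proportion with CDP or MRI activity. Its complement, less NEDA, approximates the share of patients whose only event is a relapse, subject to the discontinuation rules. That is a ceiling on this error, not a correction of it.

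**Conclusion.** The algorithm in SAP 4.4.1 is wrong as written: it can count an event that the protocol says is not a relapse. This should be corrected, but it does not threaten the primary result.

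A reader might infer that every such patient becomes a false NEDA=No, or might set the 0.3% to 3.0% directly against the 3.3-point half-width. Neither follows. That range is misclassification on the relapse component. It reaches NEDA only where the patient has no other event, and both input ranges are assumed. The illustrative NEDA effect is 0.09 to 0.9 points, with 3.0 as the upper limit. It is probably small, and it runs against the drug. ARR would be too high and time to first relapse too short. For CDP the direction differs, because an excluded episode that meets steps 1 to 3 can bar a visit within 30 days from confirming progression.

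**What to change.** Add a step to SAP 4.4.1: a reported relapse is not a protocol-defined relapse if its only symptoms are on the Protocol 4.5.4 exclusion list. State how it is applied, either from the symptoms on the relapse form or through the sponsor adjudication named in Protocol 4.5.4. Say whether it comes before the 30-day spacing step. Use the single resulting flag for NEDA, ARR and time to first relapse. Extend the CDP confirmation-visit rule to cite the new step, since it now refers only to conditions 1, 2 and 3.

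Do not require a rise in one of the six listed functional-system scores for relapses that qualify by EDSS alone. That condition is in neither document. It could also remove relapses that the protocol allows, for example bladder or cerebral deficits not on the exclusion list. It could serve to flag events for adjudication.

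The cost is a sentence of SAP text and one derived flag, or an adjudication record. Slightly fewer events will count. Deriving the flag from data assumes that the on-study relapse form records symptoms. The SAP mentions recorded relapse symptoms only for the most recent relapse before enrolment. If the on-study form does not hold them, adjudication is the workable route.
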